10. HUMAN SUBJECTS

A convenience sample of subjects undergoing limb amputation (n=60), mastectomy (n=60), knee arthroplasty (n=60), shoulder arthroplasty and rotator cuff repair (n=60), VATS (n=60), and skin grafting of the lateral thigh (n=60) will be enrolled, with an additional 20 permitted to replace drop-outs. This will total up to 380 subjects.

Inclusion criteria: Adult patients of at least 18 years of age, (1) scheduled for a primary, unilateral total knee or shoulder arthroplasty, primary unilateral rotator cuff repair, VATS procedure, skin grafting of the lateral thigh, unilateral or bilateral mastectomy, or limb amputation distal to the femoral/humeral head and including at least one metatarsal/metacarpal bone; (2) a single-injection or continuous peripheral nerve block or epidural infusion planned for perioperative analgesia; and, (3) accepting of a cryoneurolysis procedure.

Exclusion criteria: (1) chronic opioid use (daily use within the 2 weeks prior to surgery and duration of use > 4 weeks); (2) pregnancy; (3) incarceration; (4) inability to communicate with the investigators; (5) morbid obesity (body mass index > 40 kg/m²); and, (6) possessing any contraindication specific to cryoneurolysis such as a localized infection at the treatment site, cryoglobulinemia, cold urticaria and Reynaud's Syndrome.

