Randomization will be stratified by surgery type (e.g., mastectomy, upper limb amputation, and lower limb amputation). Computer-generated randomization lists will be used to create sealed, opaque randomization envelopes with the treatment group assignment enclosed in each envelope labeled with the randomization number.

The specific nerves targeted will depend on the surgical site: intercostal nerves (4 levels depending on the specific surgical approach) for mastectomy; femoral/sciatic for lower limb amputation, brachial plexus (or terminal nerves) for upper limb amputation; infrapatellar branch of the saphenous nerve for knee arthroplasty; suprascapular nerve for shoulder surgery; intercostal nerves for VATS procedures, and the lateral femoral cutaneous nerve for skin grafting of the lateral thigh. The cryoneurolysis sites will be cleansed with chlorhexidine gluconate and isopropyl alcohol. Using the optimal ultrasound transducer for the specific anatomic location and subject anatomy (linear vs curvilinear array), the target nerves will be identified in a transverse cross-sectional (short axis) view.

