Brief Pain Inventory: The Brief Pain Inventory (short form) is an instrument specifically designed to assess pain and its impact on physical and emotional functioning within the previous 24 hours.^{22,23} It has established reliability and validity, with minimal inter-rater discordance, and is recommended by

the Initiative on Methods, Measurement, and Pain Assessment in Clinical Trials (IMMPACT) consensus statement.²⁴ The Brief Pain Inventory is comprised of three domains: (1) *pain*, with four questions involving “worst”, “average”, “least”, and “current” pain levels using a 0-10 Numeric Rating Scale (NRS; 0 = no pain; 10 = worst pain imaginable); (2) percentage of *relief* provided by pain treatments with one question (reported score is the percentage divided by 10 and then subtracted from 10: 0 = complete relief, 10 = no relief); and, (3) *interference* with 7 questions involving physical and emotional functioning using a 0-10 Likert scale (0 = no interference; 10 = complete interference). The use of both single items (e.g., average pain) and the composite score (0 = optimal; 120 = worst possible) is supported by the IMMPACT recommendations for assessing pain in clinical trials.²⁵⁻²⁷

Opioid consumption

Sleep disturbances: due to surgical pain

Range of motion: measured with a standard goniometer

Forced expiratory volume in 1 second (FEV1): measured with a standard inspiratory spirometer

Cancer recurrence: for subjects who underwent the surgical procedure related to a primary cancer, subjects' records will be investigated for indications of cancer recurrence up to 3 years following catheter placement (including estrogen receptor status as + or -). Patients may be contacted by phone if records suggest that the patient has not returned to the original surgeon within the previous 12 months.

The questionnaire will differentiate among multiple dimensions of breast and limb pain:

Phantom pain: painful sensations referred to the lost body part (breast or limb).

Phantom breast/limb sensations: non-painful sensations referred to the lost body part.

Wound pain: painful sensations localized to the portion of the body still present.

Summary of post-enrollment assessments (color added for clarity)

Time Point:	Postoperative Days								Postoperative Months			
	0	1	2	3	4	7	14	21	1	3	6	12
Opioid consumption	•	•	•	•	•	•	•	•	•	•	•	•
Average & worst pain [NRS]	•	•	•	•	•	•	•	•				
Brief Pain Inventory									•	•	•	•
Average & worst phantom pain									•	•	•	•

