Incidence; duration each episode									•	•	•	•
Average & worst wound pain									•	•	•	•
Incidence; duration each episode									•	•	•	•

Difficulty sleeping due to pain?	•	•	•	•	•	•	•				
Awakenings due to pain	•	•	•	•	•	•	•				
Nausea (0=none, 10=vomited)	•	•	•	•	•	•	•				

* In addition to the above, for knee and shoulder surgery joint range of motion will be measured at various time points between 1-12 months as part of standard postoperative care; and for VATS, FEV1 will be measured at various time points during hospitalization as part of standard postoperative care.

Statistical Analysis. The limb amputation, total knee and shoulder arthroplasty, rotator cuff repair, VATS, and skin grafting subjects will be included in pilot studies to help power future clinical trials, so we will enroll a convenience sample and not have a pre-determined primary endpoint or statistical plan. However, the end points of most interest will be average pain score on postoperative day 2 for shoulder arthroplasty and skin grafting subjects, range-of-motion at 6 weeks for the rotator cuff repairs, range-of-motion for knee arthroplasty, and FEV1 for the VATS procedures.

For the subjects having mastectomy, we will power this study for an acute pain end point which will provide conclusive results for that end point; but, the data will also be used to help power a subsequent large, multicenter clinical trial for a chronic pain-related end point (which will require far more subjects than we will enroll for the current study).

For the mastectomy subjects, sample size calculations are centered around the hypothesis that cryoneurolysis decreases the incidence and severity of post-mastectomy pain in the week following surgery. To this end, the primary outcome is the average NRS (as administered as part of the Brief Pain Inventory) queried on the afternoon of postoperative day 2. The difference in the distribution of NRS between groups will be assessed using the Mann-Whitney U test. We approximate power using the two-sample t-test. Assuming a standard deviation of 2.25 NRS points,² and minimum clinically meaningful difference of 2 NRS points, n=30 patients per group provide 86% power with two-sided $\alpha=5\%$.

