The t-test approximation was confirmed by simulating integer valued NRS scores in the range 0 to 10. One group was simulated by rounding normally distributed data with mean 1.5 and standard deviation 2.5 (resulting in median of 2 and interquartile range 0 to 3); and the other with mean 3.5 and standard deviation 2.5 (resulting in median of 4 and interquartile range 1 to 5). Note these resulting summary statistics are consistent with Ilfeld et al (2014). When 10,000 trials were simulated under these assumptions, the Mann-Whitney U test provided 89.5% power, and Type I error was maintained at 4.85%.

Differences between groups in demographic variables and secondary endpoints will be assessed with the Mann-Whitney U test for continuous or ordinal data, and Fisher's Exact test for categorical data. Box-and-whisker plots will be used to visualize distributions by group.

R version 3.4.4 ([R-project.org](https://www.R-project.org)) was used for sample size calculations and simulations; and the most recent version of R will be used at the time of analysis.

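### VATS cohort: FEV1 is the end point of most interest, but extent of lung resection is neither recorded nor adjusted for, which costs precision (not validity) and leaves pilot estimates that cannot be split by resection type

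*Combined protocol and SAP*

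**What the plan says.** All references are to the combined protocol and SAP.

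- **Eligibility (section 10, Human Subjects).** The list reads "primary unilateral rotator cuff repair, VATS procedure, skin grafting of the lateral thigh". Knee, shoulder and rotator cuff operations are limited to primary, unilateral procedures, and amputation has anatomical limits. VATS has no limit on type, extent or side. None of the six exclusions concerns lung function or resection.
- **End point (section 9, Statistical Analysis).** The end points of most interest include "range-of-motion for knee arthroplasty, and FEV1 for the VATS procedures". No change-from-baseline or percent-predicted definition is given.
- **Timing (section 9, note under the assessment table).** "for VATS, FEV1 will be measured at various time points during hospitalization as part of standard postoperative care". The table lists no preoperative FEV1.
- **Allocation (section 9, after the treatment arms).** "Randomization will be stratified by surgery type (e.g., mastectomy, upper limb amputation, and lower limb amputation"). VATS is not among the examples, and no split within VATS is named.
- **Analysis (section 9, Statistical Analysis).** Outside mastectomy, the cohorts are convenience-sample pilots with no pre-set primary end point or analysis plan, intended to help power later trials. The one method given for outcomes other than the mastectomy primary is that "secondary endpoints will be assessed with the Mann-Whitney U test for continuous or ordinal data", with Fisher's exact test for categorical data. No covariate is mentioned.

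**The concern.** VATS is a surgical approach, not one operation. A cohort of 60 defined this way can combine procedures that remove no lung with wedge resections, segments and whole lobes, on one side or both. Removing lung lowers FEV1 whatever the quality of analgesia; this is basic physiology and is not stated in the documents. Postoperative FEV1 therefore mixes the signal of interest, pain-limited breathing, with a surgical effect unrelated to treatment. A preoperative FEV1 would not cure this, because the change from baseline still contains the lost lung.

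The product of this cohort is an SD and an effect estimate for a later trial. If resection type is not captured, the SD can be reported only for the mix that happened to be enrolled, and the effect is estimated less precisely than the same 60 subjects would allow.

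**Working it through.** **Inputs from the documents.** VATS n = 60, with no sample size calculation behind it, so there is no VATS figure to reproduce. The document's only power calculation is for mastectomy and does not enter here.

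**Assumptions (not in the documents).** 1:1 allocation, so 30 per arm. A share p of subjects has a major resection that lowers FEV1 by s within-type SDs: p = 20% or 50% (50% is the worst case, because p(1 - p) is largest there) and s = 0.5, 1.0 or 1.5. True treatment effect 0.75 within-type SD, the same in every resection type. Planned resection equals the resection performed.

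**Step 1: variance.** Ratio of pooled to within-type variance: V = 1 + p(1 - p)s². For p = 0.5, s = 1: 1 + 0.25 × 1 = 1.25. For p = 0.2, s = 1.5: 1 + 0.16 × 2.25 = 1.36.

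**Step 2: standard error of the difference.** With a single resection type, √(2/30) = 0.258 SD. Unadjusted with mixing, 0.258 × √V.

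**Step 3: power at two-sided 5%.** Unadjusted Mann-Whitney by simulation, with resection type left to chance.

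| p | s | V | SE, unadjusted | Mann-Whitney power |
|---|---|---|---|---|
| 20% | 0.5 | 1.04 | 0.263 | 78% |
| 20% | 1.0 | 1.16 | 0.278 | 72% |
| 20% | 1.5 | 1.36 | 0.301 | 65% |
| 50% | 0.5 | 1.06 | 0.266 | 76% |
| 50% | 1.0 | 1.25 | 0.289 | 69% |
| 50% | 1.5 | 1.56 | 0.323 | 58% |

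A linear model adjusted for major resection gives about 79% to 82% in every row, with no stratification by resection. A longer run of 20,000 trials per case lands within 2 points of each Mann-Whitney figure. In that run, with no mixing at all, the Mann-Whitney test has about 78% to 79% power, so at s = 0.5 most of the gap to the adjusted model is the choice of test and not the resection mix.

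**Step 4: bias and type I error.** In the same simulations the mean unadjusted estimate is 0.75 for a true 0.75, and the Mann-Whitney rejection rate under no effect is about 5%. Both are as they should be.

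**Step 5: chance imbalance.** For p = 50%, the between-arm difference in the share with a major resection has SE √(0.25 × 2/30) = 0.129. A one-SE imbalance moves the FEV1 difference by 0.129 × s = 0.06, 0.13 or 0.19 SD. This is already inside the unadjusted SE: at s = 1.5, √(0.258² + 0.194²) = 0.323, the table value.

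**Step 6: the next trial.** For a 0.5 within-type SD effect at 80% power, n per arm = 2(1.960 + 0.842)²/0.5² = 62.8, so 63. Multiplying 62.8 by V and rounding up gives 66, 73 and 86 at p = 20%, and 67, 79 and 99 at p = 50%.

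**The case against.** **No formal VATS plan exists.** The protocol says outright that these pilots have none, and the Mann-Whitney sentence follows the mastectomy power text, so applying it to VATS FEV1 is an inference. This stands, and it limits the weight of the power figures: no confirmatory VATS test is being weakened. It does not remove the point. Adjustment stays open later only if resection type was captured, and nothing requires that.

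**The trial is biased, or an imbalance in lobectomies could pass for a treatment effect.** A reader might infer this, and the documents do not support it. Allocation is random, the estimate is unbiased, and chance imbalance is already counted in the ordinary standard error.

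**The pooled SD is wrong for planning.** This too might be inferred, and it goes too far. A later trial that enrols the same mix and does not adjust needs the pooled SD; the within-type SD would underpower it. The documents do not say which design the later trial will have.

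**The size is all assumption.** True. At a 0.5 SD shift the loss is small. A variance estimated on 58 degrees of freedom has a 95% range of about 0.72 to 1.49 times its value, so inflation of 6% or 25% lies inside the pilot's own sampling error.

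**Stratification is needed.** It is not: adjustment alone recovers the power. Because the surgery types are given only as examples, finer VATS strata are also not ruled out.

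**Breadth is deliberate, and FEV1 is undefined in other ways.** Mastectomy may be unilateral or bilateral, and amputation covers many levels. FEV1 timing is open, and no baseline is scheduled. Both are fair. The timing and baseline gaps add noise of their own and need separate attention; they do not make resection type irrelevant to a lung-function end point.

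**Conclusion.** The point holds as a missed gain in precision in a non-confirmatory pilot. Eligibility is open, FEV1 is the VATS outcome of most interest, and no text records or adjusts for extent of resection. Under the stated assumptions the variance inflation runs from about 4% to 56%, and unadjusted power from about 78% down to 58% against about 80% with adjustment. Where in that range the trial would fall cannot be told from the documents; the cost is slight if resection types differ by half an SD and substantial at 1.5 SD with an even mix. Validity is not in question. The more durable loss is that the pilot's SD and effect could not be broken down by resection type for a later trial with different eligibility or an adjusted analysis.

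**What to change.** 1. Add one item to the VATS case report form, completed before allocation: planned resection (none, wedge, segment or lobe; one or both sides). Use the planned and not the performed resection as the covariate, so that it stays a pre-randomisation variable.
2. State that the FEV1 difference will be estimated with a linear model adjusted for planned major resection (yes/no), or compared with a van Elteren test stratified by it.
3. Report the pooled and the within-type SD side by side, so that a later trial can take whichever matches its eligibility and analysis.

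An extra randomisation stratum within VATS is optional; it adds small cells to a cohort of 60 and is not needed for the gain.

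The cost is one data item, one degree of freedom and a line of analysis text. Section 11 says surgeons who recruit are investigators involved in the patient's care, so the planned operation should be obtainable, although the documents do not say how it is recorded. If planned and performed resections often differ, the gain will be smaller than shown. Eligibility, treatment and sample size are unchanged.

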11. RECRUITMENT AND PROCEDURES PREPARATORY TO RESEARCH

Study inclusion will be proposed to eligible patients in a preoperative surgical or anesthesia-related visit or phone call within four weeks prior to surgery—either by the surgeon or anesthesiologist, both investigators and involved in the patient's clinical care (HIPAA requirements will be adhered to). If a patient desires study participation, written, informed consent will be obtained using an IRB-approved informed consent form. Selection for inclusion will not be based on sex, race or socioeconomic status. For women of childbearing age with the possibility of pregnancy, a sample of urine is always collected for a pregnancy test prior to surgery—regardless of study participation. Pregnant patients will be excluded from study participation.

12. INFORMED CONSENT

When a prospective subject desires, they will be provided information on the study purpose and protocol, as well as have any questions answered. Candidates who meet inclusion and exclusion criteria and desire study enrollment will be scheduled for their initial treatment. Written informed consent will be attained prior to any measurements or procedures the morning of surgery. This will occur in private patient care rooms, so that subjects may feel comfortable asking questions.

We do not foresee any issues relevant to the mental capacity of the potential human subjects. Written, informed consent will be attained prior to any study procedures or measurements. Following a history and physical by the site director, subjects will have an intravenous line inserted, external monitors placed, oxygen delivered by face mask, and conscious sedation provided for perineural catheter insertion. Therefore, subjects will not be sedated until following the written, informed consent process is completed.

Subjects will be provided privacy and time for decision making both in the study description/explanation telephone call to an investigator or research coordinator, as described above; and also the morning of the initial treatment using a private patient care room to again review the study, informed consent form, and answer any remaining subject questions. As noted previously, subjects may speak with an investigator by telephone from initial contact through the morning of treatment.

Surrogate consent will not be accepted; therefore, if human subjects cannot provide consent on their own, they will not be offered study enrollment. Consent by an individual's Legally Authorized Representative is unacceptable for study enrollment. Of note, minors (age < 18 years) will not be offered enrollment. Therefore, assent will not be accepted during the informed consent process.

13. ALTERNATIVES TO STUDY PARTICIPATION

Potential study subjects may simply decline enrollment. They will still receive our standard-of-care analgesics including a continuous peripheral nerve block.

14. POTENTIAL RISKS

1. Infection. There is the potential risk of infection since subjects will have a probe inserted through the skin. Since there will be nothing left going through the skin or in the subject after the probe is withdrawn, the risk of infection is very small and there has never been a report of permanent injury due to infection following cryoneurolysis.
2. Bleeding. The probe does not have an open tip and is not particularly sharp, so there is a very low risk of having any type of bleeding as a result of treatment. However, if it was to happen, we would hold pressure until the bleeding stopped.
3. The skin where the nerve is frozen could lose or gain color if the nerve is particularly close to the surface. However, this has never been reported for deeper nerves and using the probe that will be used for this study.
4. Since a nerve will be frozen, there is the chance of nerve injury. However, in 5 decades of using cryoneurolysis on peripheral nerves, only a single case of "neuritis" (nerve irritation) has been reported in medical journals, and this resolved after a few months.
5. There is the risk of loss of confidentiality. The following procedures will be done to maintain confidentiality: written, paper forms will be kept in a locked medical office and the locked Investigational Pharmacy's files. Computerized records containing personal health information will be stored on password-protected and encrypted computers.

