Theoretical benefits of cryoneurolysis include an ultra-long duration of action without opioid involvement, no catheter management/removal, the lack of an infusion pump and anesthetic reservoir to carry, an extraordinarily-low risk of infection (approaching zero), and no risk of local anesthetic toxicity, catheter dislodgement or leakage. With a single 8-minute percutaneous cryoneurolysis procedure consisting of several freeze/defrost cycles, a truncation of sensory nerve conduction is induced for 6-8 weeks (motor neurons variable) with the complete restoration of nerve structure and function following remyelination. Cryoneurolysis offers the possibility of potent, side effect-free analgesia outlasting the surgical pain, and obviating the need for postoperative opioids.

Hypothesis 1b and 1c (persistent, post-surgical chronic pain): Following mastectomy and other painful surgical procedures, moderate to severe pain within the acute postoperative period is closely associated with subsequent persistent postsurgical pain lasting months⁶ or even years.^{7,8} Such chronic pain has an incidence of 30-73%,⁸⁻¹⁰ and is strongly correlated with depression and anxiety.¹¹ There is evidence that intense analgesia immediately following surgery may decrease the incidence and/or severity of chronic pain.^{12,13} Potent analgesia can be provided with intercostal nerve blocks in which local anesthetic is percutaneously injected adjacent to the peripheral nerves innervating the

breast.^{1,13} While single-injection nerve blocks have a duration of approximately 8 hours,¹⁴ they have been associated with a lower incidence of chronic pain 4-12 months after mastectomy.^{13,15,16} Extending the block to 60 hours can further decrease the incidence and severity of chronic pain.¹⁷

Furthermore, while the prevalence of post-mastectomy phantom breast pain—painful sensations perceived in the breast that is no longer present¹⁸—varies greatly, it has been reported as high as 44%.⁹ There is prospective clinical evidence that following upper and lower extremity amputation, continuous brachial plexus, sciatic, and femoral nerve blocks may decrease the incidence and/or severity of phantom limb pain.^{19,20} Using cryoneurolysis, a dense, multi-week peripheral nerve block may be provided, offering not only the possibility of the block outlasting the surgical pain, but enabling an opioid-free recovery and dramatically decreasing the risk of chronic pain.

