9. RESEARCH DESIGN AND METHODS

All subjects would continue to receive standard and customary postoperative analgesics, so there is no risk of subjects receiving a lower degree of analgesia than if they otherwise did not enroll in the study. The cryoneurolysis procedure will be done in addition to our current UCSD standard practice.

Study Overview

Day 0 Subjects randomized and cryoneurolysis/sham procedure administered

Days 0-4, 7, 14, 21 Pain levels, opioid consumption, and other end points collected [inspiratory spirometry for hospitalized subjects following video-assisted thoracoscopic surgery will occur at various time points as part of standard care and will be collected via EPIC]

Months 1, 3, 6, 12 Brief pain inventory administered [range-of-motion measurements following knee and shoulder arthroscopy as well as rotator cuff repair will occur at various time points as part of standard care and will be collected via EPIC]

Year 3 Cancer recurrence investigated for subjects with cancer-related procedures

Subjects will be individuals undergoing unilateral or bilateral mastectomy; upper or lower limb amputation; primary, unilateral total knee or shoulder arthroplasty; primary, unilateral rotator cuff repair; video-assisted thoracoscopic surgery; and burn-related skin grafting of the lateral thigh. Those who consent to participate in this study will have standard preoperative peripheral nerve blocks administered and catheters inserted: paravertebral blocks or a fascial plane block (e.g., erector spinae plane block) for mastectomy, femoral/sciatic for lower limb amputation, brachial plexus (or terminal nerves) for upper limb amputation; femoral or adductor canal for total knee arthroplasty; interscalene for shoulder arthroplasty or rotator cuff repair; thoracic epidural for video-assisted thoracoscopic surgery (VATS); and lateral femoral cutaneous nerve for skin grafting of the lateral thigh.

Treatment group assignment (randomization). Subjects with successfully-administered peripheral nerve blocks (defined by sensory changes in the appropriate nerve distribution) will be allocated to one of two possible treatments:

1. *cryoneurolysis*
2. *sham cryoneurolysis (placebo control)*

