Cryoneurolysis probes are available for a console neurolysis device (PainBlocker, Epimed, Farmers Branch, Texas) that either (1) pass nitrous oxide to the tip inducing freezing temperatures; or, (2) vent the nitrous oxide at the base of the probe so that no gas reaches the probe tip, resulting in no temperature change. Importantly, these probes are indistinguishable in appearance, and therefore treating physicians, subjects, and all clinical staff will be masked to treatment group assignment [only the physician/investigator performing the cryoneurolysis will be unmasked]. An angiocatheter/introducer may be inserted beneath the ultrasound transducer and directed until the probe tip is immediately adjacent to the target nerve (lidocaine 2% will be administered, as needed, to anesthetize the angiocatheter track). The angiocatheter needle will be removed, leaving the angiocatheter through which the appropriate Epimed probe will be inserted until it is adjacent to the target nerve. The cryoneurolysis device will be triggered using 3 cycles of 2-minute gas activation (active or sham) separated by 1-minute defrost periods. For active probes, the nitrous oxide will be deployed to the tip where a drop in temperature to -70°C will result in cryoneurolysis. For the sham probes, the nitrous oxide will be vented prior to reaching the probe shaft, resulting in a lack of perineural temperature change. The process will be repeated with the same treatment probe for any additional nerves (e.g., all nerves will receive either active cryoneurolysis or sham/placebo, and not a mix of the two possible treatments).

FDA Approval. Cryoneurolysis has been FDA approved since May 28, 1976, with continuous clinical use since then. The specific device used for this study, the Epimed Painblocker, has been FDA cleared for use to treat both acute and chronic pain since April 30, 1986, as a significant risk device. The Painblocker is NOT considered experimental or investigational (there is no IDE); and, we are using the device in a manner that the FDA approved of regarding the subject population and purpose (treating acute pain).

Outcome measurements (end points). Staff blinded to treatment group assignment will perform all measures and assessments, which will include:

Pain: measured on the 11-point NRS of pain intensity

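### The protocol plans no solicited collection of the four physical risks it names, and its risk and sham wording leaves out the introducer needle, pleural puncture and the extra insertions

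*Combined protocol and SAP*

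**What the plan says.** **Risks.** Section 14 lists infection, bleeding, skin colour change and nerve injury, plus loss of confidentiality. On bleeding it argues: "The probe does not have an open tip and is not particularly sharp, so there is a very low risk". The planned response to a bleed is pressure.

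**Procedure.** Section 9 states: "An angiocatheter/introducer may be inserted beneath the ultrasound transducer and directed until the probe tip is immediately adjacent to the target nerve". It continues: "The angiocatheter needle will be removed, leaving the angiocatheter through which the appropriate Epimed probe will be inserted". The targets include "intercostal nerves (4 levels depending on the specific surgical approach) for mastectomy", and intercostal nerves again for VATS. Sham probes are placed in the same way, with the gas vented before it reaches the shaft. On how this relates to usual care: "The cryoneurolysis procedure will be done in addition to our current UCSD standard practice". Usual care for mastectomy is "paravertebral blocks or a fascial plane block (e.g., erector spinae plane block) for mastectomy".

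**Masking.** Among those involved, "only the physician/investigator performing the cryoneurolysis will be unmasked".

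**Data collection.** The assessment summary in section 9 covers opioids, pain, the Brief Pain Inventory, phantom and wound pain, sleep and nausea. A footnote adds range of motion and FEV1.

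**Safety follow-up.** Section 15 gives monitoring during treatment, contacts to month 12, a 24-hour physician line for at least the first week, and IRB reporting of adverse events. Section 18 repeats the IRB route.

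**Sham subjects.** Section 17 says that, for them, taking part is the same as declining, and concludes that they can expect no direct benefit.

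**The concern.** Section 9 says the mastectomy cohort will be conclusive for acute pain, and section 18 justifies the study by a low complication rate. Readers will therefore weigh a measured benefit against harms that the protocol does not say will be asked about. If the schedule is followed as written, a report of no complications cannot be told apart from a lack of enquiry.

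The risk text also does not match the procedure. A closed, blunt probe is a sound reason to expect little bleeding from the probe, but says nothing about a needle directed to the nerve before it. Intercostal nerves lie close to the pleura (general anatomy; the documents do not discuss it), and holding pressure is no response to a pleural puncture.

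Sham subjects carry the insertion risk with no expected benefit, so the statement of what they undergo should be accurate.

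**Working it through.** **1. Named risks against scheduled items.** The schedule rows are: opioid consumption; average and worst pain; Brief Pain Inventory; phantom pain; its incidence and duration; wound pain; its incidence and duration; difficulty sleeping; awakenings; nausea. That is 10 rows.

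| Risk (section 14) | Matching row |
|---|---|
| Infection | none |
| Bleeding | none |
| Skin colour change | none |
| Nerve injury | none (pain rows may reflect it, but cannot separate it from surgical pain) |

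So 0 of 10 rows match any of the 4 risks. Nausea is the only adverse effect scheduled.

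**2. Contacts available (section 15).** Days 1–4 (4) + days 7, 14, 21, 28 (4) + months 3, 6, 12 (3) = 11 per subject. For 60 mastectomy subjects: 11 × 60 = 660. The gap is in what is asked, not in the number of opportunities.

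**3. Added insertions in mastectomy.** Inputs: n = 60 (section 10), 30 per arm and 4 levels (section 9). Assumption: one insertion per level; the documents do not say this.
- One side only: 60 × 4 = 240, of which sham 30 × 4 = 120.
- If all were treated on both sides (the mix is not given): 60 × 8 = 480, of which sham 30 × 8 = 240.

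VATS adds more, but the number of levels is not stated.

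**4. What active collection could show.** With 0 events in n, the exact two-sided 95% upper limit is 1 − 0.025^(1/n).
- Both arms pooled, n = 60: 1 − 0.025^(1/60) = 6.0%.
- One arm, n = 30: 1 − 0.025^(1/30) = 11.6%.

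Fisher's test at 30 v 30, two-sided, with all k events in one arm: p = 2 × C(30,k)/C(60,k).
- 5 v 0: 2 × 142,506/5,461,512 = 0.052.
- 6 v 0: 2 × 593,775/50,063,860 = 0.024.

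A between-arm test would need 6 v 0 to reach 5%, so by-arm reporting should be descriptive. No event rate is assumed anywhere.

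**5. Timing of questions and masking.** Section 7 expects sensory loss for 6–8 weeks: 6 × 7 = 42 to 8 × 7 = 56 days. Month 3 is about day 90, so a deficit found then lies outside the intended effect. Asking sooner would mostly detect the intended numbness and could reveal the arm. Skin change is also freezing-related. A day 1 answer could hint at the arm before the primary pain score on day 2, so that question must wait until the score is recorded.

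**The case against.** The strongest reply is that this argues from silence. The schedule is a summary of outcome measures, introduced as what assessments will include, and the contacts sit under risk management, next to the physician line and adverse-event reporting. They may well be meant as safety calls. This limits the claim: a reader might infer that complications will be recorded only if a subject or clinician raises them, but the case report forms were not available and the documents do not establish that. What stands is that the protocol specifies no complication questions.

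Nor should a reader infer that adverse events go unreported. Sections 15 and 18 give an IRB route. What is missing is a plan to summarise complications in the results.

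It may also be said that vessel puncture is covered. Its consequence largely is, because section 14 lists bleeding and a response to it. The introducer is also optional. The remaining defect is that the stated reason does not extend to the needle where one is used. Pleural puncture is not covered at all.

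On section 17, the sentence stands under benefits and leads to a correct conclusion about benefit, and section 14 does not limit probe insertion to the active arm. The sham risk is therefore not hidden. The sentence is still untrue of procedural exposure. It would be wrong to infer that subjects are misinformed, because the consent form was not available.

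Finally, 60 subjects cannot say much about rare complications. That is true, and it is a reason for descriptive reporting with intervals, not for leaving the questions out.

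**Conclusion.** The point holds as a gap in specified safety collection and as two inaccuracies of wording. All four named physical risks lack a scheduled item, although 11 contacts are already planned. Section 14 rests its bleeding reassurance on the probe alone and does not name pleural puncture for mastectomy or VATS. Section 17 overlooks insertions that section 9 adds for sham subjects.

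The primary endpoint, power and type I error are not affected, and nothing here suggests that the device is unsafe. The conclusion rests on the protocol text only. Two assumptions enter: that intercostal nerves lie near the pleura (general anatomy), and, for the insertion counts alone, one insertion per level. The change should be made, but the main analysis does not depend on it.

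**What to change.** 1. **Collection.**
   - Day 0: the unmasked operator records pleural puncture and bleeding or hematoma, and whether each was seen after the standard block or after the study insertion. A paravertebral block also passes near the pleura (general anatomy), so attribution needs this note. Keep the record from masked staff.
   - From day 1: masked staff ask, after the pain items, about bleeding or hematoma, infection and any diagnosed pleural puncture.
   - Skin change: ask only once the day 2 primary score is recorded, for example from day 7.
   - Persistent sensory or motor deficit: ask at months 3, 6 and 12. Earlier spontaneous reports still go through the existing adverse-event route.
2. **Reporting.** Summarise insertion complications pooled over both arms, and freezing-related ones by arm, descriptively with exact confidence intervals.
3. **Section 14.** Cover the introducer needle, and pleural puncture at intercostal sites.
4. **Section 17.** Say that sham subjects expect no direct benefit but undergo the same insertions.

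**Cost.** There is no new visit or procedure: one short item at planned contacts, one operator line, and wording in two sections. The downsides are slightly more data, a less favourable risk statement, a small chance that later skin-change answers hint at the arm for secondary outcomes, and harm estimates that remain imprecise.
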